### **5.2.3. Additional Analyses of the Primary Endpoint**

The statistical methods for the main analysis will be repeated using the PP population. The analysis will also be performed using the observed data without imputation for missing in both the ITT population and the PP population.

Another exploratory MMRM analysis for the primary endpoint will be performed with factors for the duration of current episode of patchy alopecia (< 2 years, >= 2 years) and the treatment by duration of episode interaction replacing the baseline SALT score group and treatment by SALT group interaction factors. This analysis will be performed in both the ITT population and the PP population using data with LOCF imputation.

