1. AMENDMENT HISTORY

Protocol Version 2.0 dated 26JUL2017 was implemented prior to initiation of the study. Protocol Version 3.0 was amended to extend treatment from 3 to 6 months, add visits at Months 4, 5, and 6, allow subjects who normally shave their scalp to shave their scalp and maintain the same hair style, as long as they refrain from shaving at least 1 week prior to the study assessments or longer at the discretion of the investigator based on visible scalp hair growth and to add a requirement for sexually active males to use a barrier method of birth control (Inclusion criterion #13).

Protocol Version 4.0 dated 26APR2018 was amended to:

- clarify the definition of stable AA,
- update the ANC and platelet criteria to less than the lower limit of normal,
- add a 6-month washout period for JAK inhibitors (oral and topical),
- reduce the timeframe a WOCBP should be on highly effective birth control from 90 days to 30 days prior to study entry, given the proven onset of contraceptive effectiveness,
- update Sponsor address,
- add Sponsor Safety Monitor Contact Information,
- minor clarifications and typographical edits,
- addition of the Global Impression of Change (Physician and Subject) Assessment.

Protocol Version 5.0 dated 11JUN2018 was amended to allow enrollment of a broader range of subjects with AA for whom there is a hypothesis to support an efficacious response to ATI-50002 by:

- Decreasing the minimum SALT score from 30% hair loss to 15% hair loss,
- Increasing the maximum duration of the current episode of AA from 7 years to 12 years,
- Allowing the inclusion of subjects with ophiasis pattern of AA.
- Changing the primary efficacy analysis from the “change from baseline” to the “mean relative percent change from baseline” in the SALT score at Week 24 (Visit 10).
- Adding that the statistical analysis will include a stratification of subjects based on baseline SALT score, where the number and range of each stratum will be determined by a blinded review of the distribution of the baseline scores, conducted prior to database unblinding.
- Revising the secondary analysis:
 - Changed the “mean change from baseline” to the “mean relative percent change from baseline” in the ALODEX score
 - Added the mean change from baseline in SALT score and ALODEX score at Week 24 (Visit 10)

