2.1. Summary

Overview of Alopecia Areata

Alopecia areata (AA) is an autoimmune dermatologic condition, which, in its mildest form, is typically characterized by patchy non-scarring hair loss on the scalp and/or body. More severe forms of AA include total scalp hair loss, known as alopecia totalis (AT), and total loss of all the hair on the scalp and body- importantly, including loss of eyebrows, eyelashes, and intranasal hair-known as alopecia universalis (AU). While spontaneous regrowth of hair is common in the milder form of AA (patchy), where the hair loss may wax and wane, in patients with the extensive hair loss of AT or AU, spontaneous hair regrowth is rare. AA affects both males and females across all ethnic groups, with a lifetime risk of 1.7% (Safavi 1995). About two-thirds of affected individuals are 30 years old or younger at the time of disease onset.

The course of AA is unpredictable and while up to 50% of patients may recover within 1 year even without treatment, most patients will have more than one episode of hair loss (Price 2008). Factors portending a poorer prognosis for regrowth are more extensive hair loss presentations (extensive AA, AT, AU), an ophiasis pattern of hair loss, a long duration of hair loss, a positive family history, the presence of other autoimmune diseases, nail involvement, and young age of first onset (Tosti 2006, Weise 1996). In children, the disease may have a tendency towards worsening with time even if the initial presentation was mild, and the progressively disfiguring nature of the disease can be psychologically devastating. AA is highly associated with numerous psychiatric comorbidities including adjustment disorders, anxiety disorders and depression in both children and adults, and an effective treatment for AT and AU, the more severe forms of the disease, represents a significant unmet medical need (Bilgic 2014, Ruiz-Doblado 2003, Alkhalifah 2010).

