### **3. GENERAL STATISTICAL CONSIDERATIONS**

#### **3.1. SAMPLE SIZE AND POWER**

The planned sample size is 120 subjects. Since this is the first multicenter study evaluating the effect of ATI-50002 Topical Solution in subjects with stable patchy alopecia areata, the sample size was based upon feasibility issues rather than on a formal power calculation. However, data from 120 subjects (40 per group), utilizing LOCF for missing data, provides 80% power to detect a 24-point difference in percent change from baseline in SALT score between any two treatment groups. This power computation was based upon the assumed standard deviation of 38%. Data from a previous study NCT02197455 showed that the standard deviation in percent change from baseline in the SALT score is 30.3%. The 38% standard deviation assumption used for this power computation was chosen to account for the increase in variance due to the lower baseline SALT entry criteria for this study as compared to NCT02197455.

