### **5.2.2. Primary Efficacy Analysis**

Descriptive statistics for the SALT score, change, and percent change from baseline will be presented for each scheduled analysis visit. Percent change from baseline in SALT over time up to Week 24 will be analyzed using a mixed effect for repeated measures (MMRM) model. This primary analysis will utilize the score with imputation for LOCF and will be based on the ITT population. The model will include fixed effect terms for treatment, study visit, baseline SALT score group (<50, >=50), and treatment by SALT group interaction. Within-subject variability will be modeled using a compound symmetry covariance structure. The least squares mean (LS Mean) percent change from baseline in the SALT score at each visit, estimated from the MMRM model, with the estimated standard error and 95% confidence interval (CI), will be presented in tabular and graphic format. The difference in the adjusted means between treatment groups and the associated 95% CI of the difference will be provided.

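### No planned model adjusts for episode duration and extent of hair loss together: the primary MMRM omits duration, and the exploratory duration model drops baseline SALT

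*SAP*

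**What the plan says.** Protocol 2.1 puts extent and duration in the same prognostic sentence: "Factors portending a poorer prognosis for regrowth are more extensive hair loss presentations (extensive AA, AT, AU), an ophiasis pattern of hair loss, a long" (the sentence goes on to duration of hair loss, then family history, other autoimmune disease, nail involvement and early onset). Protocol 5.3 admits current episodes of 6 months to 12 years. The Version 5.0 entry in the amendment history records the widening: "Increasing the maximum duration of the current episode of AA from 7 years to 12 years".

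Protocol 7.2 and SAP 3.2 allocate 1:1:1 by ascending kit number and name no stratification factor.

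For the primary analysis, SAP 5.2.2 states: "The model will include fixed effect terms for treatment, study visit, baseline SALT score group (<50, >=50), and treatment by SALT group interaction". Protocol 11.4.1 lists the same terms. Duration is absent. SAP 5.2.3 adds one exploratory MMRM, in ITT and PP with LOCF, containing duration of the current episode (<2, >=2 years) and its interaction with treatment, "replacing the baseline SALT score group and treatment by SALT group interaction factors". SAP 5.1 summarises duration at baseline, both continuous and dichotomised. The subset analyses in SAP 5.2.7 use SALT group and whole-scalp treatment, and the responder model in SAP 5.2.5 has treatment and SALT group only.

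**The concern.** The protocol treats duration and extent as separate prognostic factors, but the plan never lets them into one model. The same amendment lowered the SALT floor and raised the duration ceiling. The wider SALT range is reflected in a model term and in a larger assumed SD (38 instead of 30.3, SAP 3.1). The wider duration range is reflected in neither.

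Two things follow. First, with about 40 subjects per arm, the shares of shorter and longer episodes can differ between arms by chance. The primary model would not adjust for that difference, and variance due to duration would stay in the error term. Second, a reader of the exploratory model could not tell whether a duration effect, or a treatment-by-duration effect, is distinct from extent. The plan also does not say what happens if duration turns out imbalanced, so any joint adjustment would be chosen after unblinding.

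**Working it through.** **Inputs from the documents.** 40 per group, SD 38, difference 24, two-sided 0.05 (SAP 3.1 and 5).

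**Inputs assumed.** The documents give no duration effect, no share of subjects at 2 years or more, and no correlation between duration and SALT group. I take a prognostic gap *b* of 10, 20 or 30 points between duration groups, a share *p* of 30% to 70% at 2 years or more, and a correlation φ of 0 to 0.4. The formulas are for a two-group Week 24 comparison, as in the sample-size section, not for the full repeated-measures model.

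**1. The plan's own figure.** SAP 3.1 claims that "data from 120 subjects (40 per group), utilizing LOCF for missing data, provides 80% power to detect a 24-point difference".
- SE of the difference = 38 × √(2/40) = 8.50.
- Power = Φ(24/8.50 − 1.96) = 80.6% (noncentral t: 79.7%).
- Detectable difference = (1.96 + 0.842) × 8.50 = 23.8 (t: 24.1).

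The claim reproduces.

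**2. Chance imbalance.** The SD of the difference in shares is √(2p(1−p)/40). This is 0.112 at p = 0.5 and 0.102 at p = 0.3 or 0.7, so the 95% range is about ±20 to 22 percentage points. From the exact difference of two Binomial(40, p) counts, P(at least 20 points) is 9.3% at p = 0.5 and 6.7% at p = 0.3 or 0.7. For at least one of the two active-vehicle comparisons it is 12% to 16%.

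**3. Consequence and gain at p = 0.5.**
- R² = b²p(1−p)/38².
- Residual SD = 38 × √(1−R²).
- Shift at a 20-point imbalance = 0.20 × b.
- The conditional columns describe the comparison without a duration term. They use the critical value 1.96 × 8.50 = 16.65 and a conditional SE of residual SD × √(2/40). Conditional power, when the imbalance goes against the drug, is 1 − Φ((16.65 − 24 + shift)/conditional SE).

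| b | R² | Residual SD | Power for 24, adjusted | Detectable difference | Shift | Conditional type I error | Conditional power |
|---|---|---|---|---|---|---|---|
| 10 | 1.7% | 37.7 | 81.3% | 23.6 | 2 | 5.4% | 74% |
| 20 | 6.9% | 36.7 | 83.3% | 23.0 | 4 | 6.7% | 66% |
| 30 | 15.6% | 34.9 | 86.7% | 21.9 | 6 | 8.8% | 57% |

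The shifts are 2/8.5 = 0.24, 4/8.5 = 0.47 and 6/8.5 = 0.71 of a standard error.

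**4. Average behaviour.** I simulated a Week 24 ANCOVA with 40 per arm, 6,000 runs per setting, a SALT-group effect of 10 points and φ of 0 or 0.3. The SALT-only, duration-only and joint models all gave mean estimates within 0.3 of the truth and type I error of 4.7% to 5.7%. At b = 30, power rose from 79.7% (SALT only) to 85.5% (joint) with φ = 0, and from 81.6% to 86.6% with φ = 0.3. At b = 10 there was practically no gain (78.6% to 79.0%; 80.0% to 79.8%).

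**5. What the duration terms absorb when SALT is dropped.** With even splits, P(SALT ≥50 | long) − P(SALT ≥50 | short) = φ. A SALT-group effect of *g* points therefore puts φ × g into the duration term, and a treatment-by-SALT effect of *g* puts the same amount into treatment-by-duration. For g = 10 to 30 this is 0 at φ = 0, 2 to 6 points at φ = 0.2, and 4 to 12 points at φ = 0.4.

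**The case against.** The case against is substantial, and much of it stands.

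- **A reader might infer that imbalance in duration goes uncorrected.** The plan as a whole does not support that. The SAP 5.2.3 model gives a treatment contrast adjusted for duration, and the SAP 5.1 table would show an imbalance. What is missing is adjustment for both factors at once, and any duration adjustment in the primary analysis.
- **A reader might infer that the primary estimate is biased.** It is not. Omitting a prognostic covariate leaves a randomised comparison unbiased on average, and the standard error already allows for chance imbalance. A 6-point shift needs both an assumed 30-point effect and an imbalance with probability of about 9%.
- **A reader might infer that duration is confounded with extent.** The documents list both as prognostic but report no correlation. If there is one, it affects the duration and treatment-by-duration terms of one exploratory model, not the randomised treatment contrast. The SALT term in the primary model would then also absorb part of a duration imbalance, so the shifts above would be smaller.
- **Natural course.** The protocol says that "up to 50% of patients may recover within 1 year even without treatment", but this describes patients generally. Entrants must have had at least 6 months of hair loss and no current spontaneous regrowth, so the figure cannot be carried over to them. The prognostic sentence also refers to duration of hair loss, not explicitly to the current episode.
- **The 2-year cut.** The extension from 7 to 12 years lies wholly above it, and recovery within a year wholly below it. The split captures neither contrast.
- **Choice of covariate.** The protocol lists other prognostic factors too, and this is a Phase 2 study sized on feasibility. Duration differs in that the SAP already dichotomises it and gives it its own model.

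None of this explains why the SALT terms must leave when duration enters.

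**Conclusion.** The point holds in a limited form, with minor to moderate severity. No planned analysis adjusts for duration and extent together, although the protocol names both as prognostic and both are collected. The primary analysis remains valid on average, and the sample-size statement is unaffected.

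The loss is modest precision (under 1 to about 6 points of power for a 24-point difference) and exposure to a shift of 2 to 6 points if a 20-point imbalance occurs. These sizes rest on the assumed duration effect and share of longer episodes. They also assume no overlap between duration and SALT group, so they are towards the high end if the two are correlated. Whether the exploratory duration terms would be contaminated by extent depends on a correlation that the documents do not give; it is a risk, not a finding.

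**What to change.** Before unblinding:

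1. In SAP 5.2.2, Protocol 11.4.1 and the matching synopsis text, add duration of current episode (<2, >=2 years) as a main effect beside SALT group and treatment-by-SALT group.
2. In SAP 5.2.3, fit duration and treatment-by-duration with both SALT terms retained instead of replaced.

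If the primary model is to stay as it is, prespecify the joint model as a sensitivity analysis.

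The cost is one model statement in each document and one degree of freedom in the primary model. The data are already collected and the split already defined. The 2-year split will leave some duration-related variation unadjusted. Continuous duration, which SAP 5.1 already summarises, could be prespecified as a sensitivity version.

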### **5.2.4. Secondary Efficacy Endpoints**

The secondary efficacy endpoints include:

- Mean percent change from baseline in the ALODEX score at Week 24 (Visit 10), also described as mean percent regrowth,
- Mean change from baseline in SALT score at Week 24 (Visit 10)
- Mean change from baseline in ALODEX score at Week 24 (Visit 10)
- Proportion of subjects in each treatment arm achieving  $\geq 50\%$  hair regrowth compared with baseline using a separate model for SALT and for ALODEX scores
- Change from baseline in the Scalp-PRO at Week 24 (Visit 10)
- Change from baseline in the Scalp-ClinRO at Week 24 (Visit 10)
- Change from baseline in the PhGIS of Patchy AA at Week 24 (Visit 10)
- Change from baseline in the SGIS of Patchy AA at Week 24 (Visit 10)
- Change from baseline in the subject reported AIA-PRO at Week 24 (Visit 10)
- SGITS at Week 24 (Visit 10)
- Change in DLQI total score between Baseline and Week 24 (Visit 10)
- PhGIC at Week 24 (Visit 10)
- SGIC at Week 24 (Visit 10)

### **5.2.5. Secondary Efficacy Analysis**

Descriptive statistics will be presented for all secondary efficacy endpoints.

The mean percent change from baseline in the ALODEX score (percent regrowth); the mean change from baseline in SALT and the mean change from baseline in ALODEX will be analyzed using the methods planned for the primary efficacy analysis. The calculated DLQI total score ranges from 0 to 30. This mean change from baseline in DLQI will also utilize the MMRM analysis as planned for the primary efficacy analysis.

Responder-type analyses are planned based on the SALT, ALODEX, Scalp-ClinRO, and Scalp-PRO. The responder definitions include:

- The proportion of subjects achieving a  $\geq 50\%$  hair regrowth compared with baseline for SALT and for ALODEX scores
- Proportion of subjects achieving an absolute SALT score  $\leq 10$
- Proportion of subjects with  $\geq 2$ -point improvement in Scalp-ClinRO for the Target Area
- Proportion of subjects with  $\geq 2$ -point improvement in Scalp-PRO for the Target Area
- Proportion of subjects with  $\geq 1$ -point improvement in Scalp-ClinRO for the entire scalp
- Proportion of subjects with  $\geq 1$ -point improvement in Scalp-PRO for the entire scalp

The observed proportion of responders and associated 95% CI will be presented. Adjusted rates and 95% CI will be obtained from a logistic regression model with factors for treatment and baseline SALT score group. The p-value for the overall global test that  $\beta = 0$  for each factor will be presented. The adjusted odds ratios (95% CI) for being a responder (active/vehicle) will be presented along with the associated p-value.

The questionnaires Scalp-PRO, Scalp-ClinRO, PhGIS, and SGIS are collected on a 1-5 scale. The frequency of responses for each value will be reported by visit and treatment group. Additionally, change status will be categorized as “Better by x points” when the score decreases from baseline by x points, and as “Worse by x points” when the score increases by x points. For these scales, a stratified Wilcoxon rank sum test will be used at each visit to obtain a p-value to compare the change status of each active treatment group to the vehicle.

For SGITS, PhGIC, and SGIC, the frequency of responses will be summarized for each scheduled collection timepoint. A stratified Wilcoxon rank sum test will be used at each visit to obtain a p-value to compare the results of each active treatment group to the vehicle.

The AIA-PRO consists of 13 questions each rated on a scale of 1 to 10 and mean total score. The mean total score is taken as the average of the 13 items. If any of the items is missing the mean total score will not be calculated. Descriptive statistics for actual and change from baseline for the mean total score and each individual item will be presented.

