5.3. Double-Blind Inclusion Criteria

Subjects must meet the following criteria to be eligible for participation in the study:

1. Able to comprehend and willing to sign an Informed Consent/Accent Form (ICF).
2. Male or non-pregnant, non-nursing female ≥ 12 years old at the time of informed consent/assent.
3. Have a clinical diagnosis of stable patchy alopecia areata (AA) defined as no current areas of spontaneous regrowth.
4. Have a Severity of Alopecia Tool (SALT) score of at least 15% up to 95% total scalp hair loss determined by the study investigator at baseline.
5. Have an assessment of “no hair” or “a little hair” in the target scalp patch based on both the Clinician and Subject Alopecia Scalp Appearance Assessment (AAA).
6. Have a duration of the current episode of scalp hair loss of a minimum of 6 months and a maximum of 12 years.
7. If a woman of childbearing potential (WOCBP), must have a negative serum pregnancy test at Screening (Visit 1) and a negative urine pregnancy test at Baseline (Visit 2) and agree to: use a highly effective method of birth control for the duration of the study; not be planning a pregnancy during the study duration and use contraception for 30 days after last application of study medication. (Refer to Section 10).

8. Be in good general health and free of any known disease state or physical condition which, in the investigator's opinion, might impair evaluation of the subject or which might expose the subject to an unacceptable risk by study participation.
9. Be willing to maintain the same hair style throughout the study period. Subjects who shave their scalp must be willing to refrain from shaving their scalp for at least one week or longer prior to each study visit, as determined by the investigator based on visible scalp hair growth. Hair trimming outside the treatment areas to maintain the current hair style is permitted.
10. Be willing and able to follow all study instructions and to attend all study visits.
11. Subjects taking hormonal replacement therapies must be on stable doses for 6 months prior to enrollment and remain on the same maintenance dose throughout the study.
12. Subjects taking thyroid replacement medication must be on stable doses for 6 months prior to enrollment and remain on the same maintenance dose throughout the study.

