8.1.2. Alopecia Density and Extent Score (ALODEX)

The ALODEX score is a measurement of the amount of scalp with terminal hair loss. The investigator will calculate the ALODEX score using the iPad provided by Aclaris at baseline and monthly during the study. The ALODEX score must be determined after the SALT score. At the baseline visit (Visit 2), the ALODEX score must be determined prior to randomization. Equipment, supplies, training and the detailed Reference Guide will be provided to the investigational site prior to the initiation of subject enrollment.

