8.3.3. Dermatology Life Quality Index (DLQI)

The impact of patchy AA on the quality of life of subject will be assessed using the DLQI (APPENDIX 10) at Baseline (Visit 2), Week 4 (Visit 5), Week 12 (Visit 7), and Week 24 (Visit 10). The investigator or study staff will instruct the subject to answer the questions based on the scalp hair loss instead of skin.

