### **3.3. HANDLING OF DATA**

#### **3.3.1. Strata and Covariates**

The baseline SALT score group (<50, >=50) will be used a stratum in the planned primary efficacy models. The strata will not be used in the subset analyses.

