#### Change from Baseline

Change from Baseline for a given endpoint is defined as the value at the analysis visit minus the baseline value.

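### The DLQI and ALODEX change models leave out each endpoint's own baseline, which is already collected; adding it is an optional precision gain

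*SAP*

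**What the plan says.** SAP 5.2.5 does not write out a model for the change endpoints. It points back to the primary analysis: change in SALT and change "in ALODEX will be analyzed using the methods planned for the primary efficacy analysis", and for DLQI, "This mean change from baseline in DLQI will also utilize the MMRM analysis as planned for the primary efficacy analysis".

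The model pointed to is in SAP 5.2.2. Its fixed effects are treatment, visit, "baseline SALT score group (<50, >=50), and treatment by SALT group interaction". No continuous baseline appears. SAP 3.3.1, on strata and covariates, mentions one variable only: "The baseline SALT score group (<50, >=50) will be used a stratum in the planned primary efficacy models". Protocol 11.4.1 lists the same terms.

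The own baselines exist. Protocol 8.1.2 says of ALODEX: "At the baseline visit (Visit 2), the ALODEX score must be determined prior to randomization". Protocol 8.3.3 schedules the DLQI at Visit 2 and at Weeks 4, 12 and 24. In the change analyses these values are used only in the definition in SAP 3.3.6: "Change from Baseline for a given endpoint is defined as the value at the analysis visit minus the baseline value".

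Protocol 11.4.2 ties percent change in ALODEX to the primary method and leaves the remaining parameters to the SAP.

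**The concern.** A change score fixes the slope of follow-up on baseline at 1. If the true slope differs, part of the variation in the change score is predictable from baseline, and a model without that baseline counts it as noise. The SALT group absorbs some of it, but only as far as a two-level split of hair loss tracks the endpoint's own baseline. For DLQI, a quality-of-life score, it may track very little. For ALODEX it is a partial proxy.

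Randomisation protects against bias, so only precision is at stake: wider intervals and weaker tests for the DLQI and ALODEX change contrasts. With about 40 subjects per arm, a number set by feasibility, precision cannot easily be found elsewhere.

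**Working it through.** **The plan's own figure.** The only power figure in the documents concerns percent change in SALT: 40 per group, SD 38, difference 24, two-sided 0.05. The standard error is 38 × √(2/40) = 8.50, and 24/8.50 − 1.96 = 0.86, giving power 0.806 (0.797 with the t distribution). The stated 80% reproduces, and this point does not affect it. There is no corresponding figure for DLQI or ALODEX.

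**Inputs.** None of the following is in the documents, so each is an assumption shown over a range.

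- r: correlation between baseline and Week 24, taken as 0.3, 0.5, 0.7 and 0.9.
- s: Week 24 SD divided by baseline SD, taken as 0.8, 1.0 and 1.3. A value above 1 is plausible for the scalp scores, because entry requires subjects to "Have a Severity of Alopecia Tool (SALT) score of at least 15% up to 95% total scalp hair loss" while follow-up is unrestricted.
- g: share of the endpoint's baseline variance explained by SALT group. For DLQI, g = 0. For ALODEX, suppose SALT is uniform on 15 to 95 and is cut at 50. The total variance is 80²/12 = 533.3, and the between-group variance is (35/80)(45/80) × 40² = 393.75, a share of 0.738. With a SALT–ALODEX correlation of 0.9, g = 0.738 × 0.81 = 0.60; with 0.8, g = 0.738 × 0.64 = 0.47.

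**Formula (single visit, Week 24, baseline SD = 1).**

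- Residual variance of change, SALT group only: s²(1 − r²) + (1 − rs)²(1 − g)
- With own baseline added: s²(1 − r²)
- Cut in contrast variance = (1 − rs)²(1 − g) / [s²(1 − r²) + (1 − rs)²(1 − g)]

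The numerator is never negative, and it is zero when rs = 1.

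Example, DLQI with r = 0.5, s = 1, g = 0: 0.25/(0.75 + 0.25) = 25%. The interval shrinks by 1 − √0.75 = 13%.

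| Cut in variance, % | r = 0.3 | 0.5 | 0.7 | 0.9 |
|---|---|---|---|---|
| DLQI, s = 0.8 | 49.8 | 42.9 | 37.2 | 39.2 |
| DLQI, s = 1.0 | 35.0 | 25.0 | 15.0 | 5.0 |
| DLQI, s = 1.3 | 19.5 | 8.8 | 0.9 | 8.3 |
| ALODEX (g = 0.60), s = 0.8 | 28.5 | 23.2 | 19.3 | 20.6 |
| ALODEX (g = 0.60), s = 1.0 | 17.8 | 11.8 | 6.6 | 2.1 |
| ALODEX (g = 0.60), s = 1.3 | 8.9 | 3.7 | 0.4 | 3.5 |
| ALODEX (g = 0.47), s = 1.0 | 22.1 | 15.0 | 8.5 | 2.7 |
| SALT change (g = 0.74), s = 1.0 | 12.4 | 8.0 | 4.4 | 1.4 |
| SALT change (g = 0.74), s = 1.3 | 6.0 | 2.5 | 0.2 | 2.3 |

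As interval width, 1 − √(1 − cut), the DLQI row at s = 1.0 becomes 19, 13, 8 and 2.5% narrower. ALODEX at g = 0.60, s = 1.0 becomes 9, 6, 3 and 1% narrower.

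**Simulation check.** 3,000 runs per cell, 3 × 40 subjects, SALT group and its interaction in both models. DLQI cuts were 34.2, 23.3, 12.9 and 5.6% at s = 1.0, and 19.4, 8.4, 0.0 and 6.7% at s = 1.3. ALODEX (g = 0.60) cuts were 16.9, 11.3, 6.7 and 1.9% at s = 1.0, and 8.1, 1.9, −0.4 and 1.8% at s = 1.3. The mean contrast stayed within 0.02 baseline SD of zero with and without the covariate, so there is no bias either way.

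**Contrast averaged over visits.** SAP 5.2.2 lists no treatment-by-visit term, so its treatment effect may be read as an average over visits. With k visits, equal variances and one correlation r throughout, let m = [1 + (k − 1)r]/k. The residual variance is m + 1 − 2r − g(1 − r)² without the own baseline and m − r² with it. At r = 0.5:

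- DLQI, k = 3, g = 0.05: 0.654 against 0.417. The planned interval is about 25% wider than needed.
- ALODEX, k = 6, g = 0.5: 0.458 against 0.333, about 17% wider.

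Under these assumptions the single-visit figures understate the loss.

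**The case against.** The strongest reply is that nothing is wrong with the plan. Change from baseline with a severity group in the model is valid, pre-specified and unbiased, and one common model for every continuous endpoint is a defensible choice. No success rule depends on these endpoints. All of that stands, and it is why this is an optional improvement.

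The size is also open to challenge. Every percentage rests on assumed correlations and SD ratios. For the scalp scores, where s above 1 is plausible, the gain is small: at s = 1.3 the ALODEX variance cut is at most 8.9%, about 4.5% in interval width. Last-observation-carried-forward values may lie closer to baseline and push the slope towards 1, shrinking the gain. These limits stand too.

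A more technical objection is that the formula uses the best Week 24 slope, whereas a covariate costing one degree of freedom has one slope across visits. Taking DLQI with s = 1, g = 0 and correlations 0.9, 0.7 and 0.5 at Weeks 4, 12 and 24, the common slope for change is the mean of −0.1, −0.3 and −0.5, or −0.3. The Week 24 residual variance is then 1 − 2(0.3)(0.5) + 0.3² = 0.79, a cut of 21% rather than 25%. That trims the gain without removing it.

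Finally, SAP 3.3.1 speaks of the primary models, so its silence does not settle what the secondary models contain. The cross-reference in SAP 5.2.5 does.

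**Conclusion.** The point holds as a minor efficiency matter. Own baselines for DLQI and ALODEX are collected, are not model terms, and are represented only by the subtraction and a two-level SALT split. Precision is lost unless correlation × SD ratio equals 1.

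Over the ranges tried, the variance cut from adding the own baseline runs from about 1% to 50% for DLQI and about 0.4% to 28% for ALODEX at g = 0.60. DLQI probably has more to gain. The omission can be read directly from the documents; the size cannot, because it depends on assumed r, s and g. The worst case is roughly no gain for about one degree of freedom. The primary analysis, its power statement and its success criterion are untouched.

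**What to change.** In SAP 5.2.5, add continuous baseline DLQI to the DLQI change model, continuous baseline ALODEX to the ALODEX change model and, for consistency, continuous baseline SALT to the SALT change model. Keep SALT group and its treatment interaction in all three. State in the same paragraph that the percent-change SALT and percent-change ALODEX models keep the terms given in Protocol 11.4.1 and 11.4.2. The difference in covariates is then visibly deliberate and does not spread by cross-reference.

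The cost is an SAP edit before unblinding. No protocol amendment is needed, since Protocol 11.4.2 leaves these change analyses to the SAP, and no new data are required. Three planned tables are affected: 14.2.1.8, 14.2.2.3 and 14.2.9.2. The SALT-group subset analyses in SAP 5.2.7 use percent change and responder endpoints and stay as they are. Change and percent-change tables for the same score will carry different covariates, which the added sentence explains.
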